7.5 Analysis of Safety

7.5.1 Adverse Events

Safety will be assessed through descriptive statistics for the frequency of TEAEs by system organ class, preferred term, and the NCI CTCAE grade, the frequency of treatment discontinuations due to AEs, vital signs, ECG and laboratory evaluations.

The severity of all AEs is to be evaluated by the Investigator based on the NCI CTCAE, version 4.03. All AEs will be coded to preferred term and system organ class using MedDRA. The number and percentage of subjects with TEAEs will be presented by MedDRA system organ class and preferred term, relationship to study treatment, and NCI CTCAE grade. TEAE is defined as an AE observed during the treatment-emergent period, which is from the first dose date of study drug to 30 days after the last dose date of study drug or the start of subsequent treatment, whichever is first. A subject reporting the same AE more than once is counted once and at the maximum severity or strongest relationship to study drug treatment, when calculating incidence.

The number and percentage of TEAEs, serious TEAEs, AEs leading to discontinuation and TEAEs related to study drug will be summarized by system organ class, preferred term and treatment group. The number and percentage of TEAEs by severity will also be summarized. All AEs will be listed.

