6.2.1 Adverse Events

TEAE is defined as an adverse event observed during the treatment emergent period, which is from the first dose date of enzalutamide to 30 days after the last dose date of enzalutamide or the start of subsequent treatment, whichever is first. If the adverse event occurs on Day 1 and the onset check box is marked “Onset after first dose of study drug” or the onset check box is left blank, then the adverse event will be considered treatment emergent. If the adverse event occurs on Day 1 and the onset check box is marked “Onset before first dose of study drug”, then the adverse event will not be considered treatment emergent.

A drug-related TEAE is defined as any TEAE with at least possible relationship to study treatment as assessed by the investigator or with missing assessment of the causal relationship.

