7.4.2 Analysis of Secondary Endpoints

Similar analysis of the primary endpoint as described in Section 7.4.1 will also be conducted on the secondary endpoint PFS.

PFS is defined as the time from the date of randomization until the date of disease progression (radiographic progression) per RECIST 1.1, or death from any cause on study, whichever occurs first.

The following subjects will be censored at the date of the last radiological assessment showing no progression:

- 1) subjects who initiated another anti-tumor therapy before documented PD or death,
- 2) subjects who progressed or died after missing two or more consecutive radiological assessments.

Subjects are considered to have missed two or more consecutive radiological assessments if duration between two consecutive imaging scans are more than 20 weeks while on treatment. Subjects who have no valid post-baseline tumor assessment will be censored at day 1.

The distribution of PFS will be estimated for each treatment group using Kaplan-Meier methodology and compared between the Enzalutamide and placebo treatment groups using the stratified log-rank test. Stratification will be done by the regions (Asia versus Other) and ECOG performance status (0 versus 1). Additionally, unstratified analysis will be performed as well.

A sensitivity analysis for subjects randomized and treated will be performed if needed, depending on number of patients randomized and not treated, this will be decided at the Final Data Review if this analysis is needed or not.

A sensitivity analysis will be done if needed with similar PFS definition, and the initiation of another anti-tumor therapy will be considered as an event, and evidence of progression could come from two sources: radiographical or clinical. This sensitivity analysis will be performed only if further investigation is needed.

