7.4.3 Analysis of Exploratory Endpoints

7.5 Analysis of Safety

Safety will be assessed on an ongoing basis by physical examination, measurement of vital signs, laboratory assessments, 12-lead ECGs, and evaluation of TEAEs/serious TEAEs.

Safety analyses will be conducted using the SAF. The SAF is defined as all subjects who have initiated at least 1 or partial capsule of study drug. The treatment emergent period will be defined as the period of time from the first dose date of study drug to 30 days after the last dose date of study drug or the start of subsequent treatment (whichever is first). Only data within this period will be summarized in safety analysis. Safety will be assessed through descriptive statistics for the frequency of adverse events by system organ class (SOC), preferred term (PT), and NCI CTCAE grade, the frequency of treatment discontinuations due to adverse events, vital signs, ECG, and laboratory evaluations.

All safety summaries will be provided using the SAF population.

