10.1.2 Progression-Free Survival

Progression-free survival (PFS) is defined as the time interval from the date of randomization to the date of disease progression as determined by the investigator using RECIST 1.1 or the date of on-study death due to any cause, whichever occurs first. Please refer to section 7.4.2

Patients who die after receiving the first dose of enzalutamide without postbaseline tumor assessments evaluable using RECIST 1.1, will be considered to have a PFS event on the date of death.

The censoring rules for the primary and sensitivity analyses of PFS are summarized in the following table. The earliest of the following censoring times will be used:

Analysis	Censoring Rules	Date of Censoring
Primary analysis of PFS	No evaluable post-baseline imaging assessments, nor death	Date of randomization
	No radiographical progression nor death before analysis cutoff date	Date of last radiological assessment before analysis cutoff date
	No radiographical progression nor death before new HCC treatment	Date of last radiological assessment before start of new HCC treatment

10.1.3

[REDACTED]	[REDACTED]	[REDACTED]
[REDACTED]	[REDACTED]	[REDACTED]
	[REDACTED]	[REDACTED]
	[REDACTED]	[REDACTED]

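### SAP 7.4.2 and SAP 10.1.2 give conflicting PFS rules for subjects who die without a post-baseline tumor assessment

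*SAP*

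**What the plan says.** **PFS.** SAP 7.4.2 defines PFS with death on study as an event, then adds: "Subjects who have no valid post-baseline tumor assessment will be censored at day 1". It states no exception for a subject who has died.

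SAP 10.1.2 also counts death on study, whatever the cause and in either arm. The first row of its censoring table applies only when there is neither evaluable imaging after baseline nor a death. Between the definition and the table is a separate sentence on early deaths: "Patients who die after receiving the first dose of enzalutamide without postbaseline tumor assessments" are to have a PFS event on the date of death. Taken alone, that sentence covers enzalutamide-dosed patients only.

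SAP 6.1.2 sends the reader to Appendix 10.1 for the censoring rules, and 10.1.2 sends the reader back to 7.4.2. Protocol 7.4.2 leaves the detailed censoring rules to the SAP.

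**Treatment-emergent window.** SAP 6.2.1 runs the window "from the first dose date of enzalutamide to 30 days after the last dose date of enzalutamide". SAP 7.5 runs the same period "from the first dose date of study drug to 30 days after the last dose date of study drug" and adds "Only data within this period will be summarized in safety analysis". Protocol 7.5.1 likewise has "which is from the first dose date of study drug to 30 days after the last dose date of study drug". The Day 1 check-box rule inside SAP 6.2.1 also refers to study drug: "Onset after first dose of study drug".

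**The concern.** A programmer who follows SAP 7.4.2 as written removes from PFS every subject who died before a first scan. One who follows the 10.1.2 table counts each of those deaths as an event. These are among the worst outcomes in the trial, and in advanced HCC after sorafenib they will not be rare. The choice changes the number of PFS events and the Kaplan-Meier curves, and the SAP leaves it open.

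The early-death sentence in 10.1.2 adds to the difficulty. It reads as an exception to 7.4.2, but its wording reaches only one arm and only dosed subjects, whereas the FAS includes every randomized subject, treated or not.

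The wording in 6.2.1 is a lesser matter: one period is defined in two ways within the SAP.

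**Working it through.** **1. The rules side by side.** Take a randomized subject who dies on study with no post-baseline scan.

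| Reading | Dosed, enzalutamide | Dosed, placebo | Never dosed |
|---|---|---|---|
| 7.4.2 alone | censored at day 1 | censored at day 1 | censored at day 1 |
| 10.1.2 definition and table | event | event | event |
| 10.1.2 early-death sentence as an exception to 7.4.2 | event | censored at day 1 | censored at day 1 |

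The first two rows contradict each other but treat the arms alike. Only the third depends on the arm, and it requires setting aside the definition and table in 10.1.2.

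**2. The plan's own figures.** The SAP gives no figure for PFS. Its OS design uses medians of 7.0 and 10.77 months (7.0/10.77 = 0.65), 2:1 allocation, one-sided alpha 0.10, and 109 deaths for 80% power (SAP 4). Schoenfeld's formula gives (1.2816 + 0.8416)² / [(2/3)(1/3)(ln 0.65)²] = 4.508/0.04124 = 109.3, and 109 deaths give 79.9% power. The design reproduces, and nothing below alters it.

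**3. How many subjects could be affected.** Inputs are those medians, 165 subjects enrolled (protocol synopsis), taken as 110 and 55 at 2:1, and scans every 8 weeks ± 7 days. Assumptions are exponential survival and no imaging in anyone who dies before the first scheduled scan. Eight weeks is 56/30.4375 = 1.84 months, and P(death by t) = 1 − 2^(−t/median).

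- Placebo: 1 − 2^(−1.84/7.0) = 16.7%; × 55 = 9.2.
- Enzalutamide: 1 − 2^(−1.84/10.77) = 11.2%; × 110 = 12.3.
- First scan between day 49 and day 63: 8 to 10 on placebo, 11 to 14 on enzalutamide.

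**4. Effect of 7.4.2 taken literally in both arms.** About 9 + 12 = 21 deaths leave the PFS analysis. Censoring at day 1 amounts to excluding these subjects. Apart from other censoring, the PFS curve after the first scan is therefore multiplied by 1/(1 − share dropped): 1/(1 − 0.167) = 1.20 on placebo and 1/(1 − 0.112) = 1.13 on enzalutamide. PFS looks better than it was in both arms.

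**5. Effect of the mixed reading.** This was illustrated with a large simulation (30,000 subjects, 2:1) with no true effect, median OS of 7 months in both arms, and median time to latent progression of 2, 3, 4 or 6 months, detected at 8-weekly scans. With one rule for both arms, the Cox HR was 0.99 to 1.01. With early placebo deaths censored at day 1 and early enzalutamide deaths counted, it was 1.18 to 1.20, against enzalutamide. Under the 10.1.2 definition and table there is no such shift.

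**The case against.** The best defence is that the SAP already gives the right answer. The 10.1.2 definition has no arm restriction, its table requires the absence of death before censoring, and 6.1.2 names Appendix 10.1 as the place for censoring rules. The early-death sentence says that certain deaths are events; it does not say that others are not. On this view 7.4.2 merely omits a few words, and enzalutamide is a slip for study drug.

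Much of this stands. A reader might infer from 10.1.2 that PFS is biased against enzalutamide by rule. The documents do not support that, because 7.4.2 alone and the 10.1.2 definition and table each treat the arms alike.

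A reader might also infer from 6.2.1 that placebo subjects can have no treatment-emergent events, leaving their columns blank. That does not follow either. SAP 7.5 governs the safety summaries and uses study drug, as does the protocol, and the Day 1 rule in 6.2.1 itself admits placebo events.

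The counts are upper-end figures. Unscheduled scans are allowed, and entry requires an estimated life expectancy of at least 3 months.

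The defence does not remove the conflict over early deaths. Section 7.4.2 is a plain instruction in the main analysis section, and 10.1.2 refers back to it. If the definition already overrode it, the early-death sentence would not be needed.

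**Conclusion.** The conflict is real, and the censoring sentence in SAP 7.4.2 is wrong as written: applied literally, it discards deaths that the endpoint definition counts. Up to about 9 of 55 placebo and 12 of 110 enzalutamide subjects could be affected. That rests on exponential survival at the design medians, exact 2:1 allocation of 165 subjects, and no scan before week 8 in those who die; the true number is probably smaller.

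An HR shift to about 1.2 under no effect belongs only to the mixed reading and is not what the SAP as a whole prescribes. The intended rule is recoverable from the 10.1.2 table, so this should be corrected, but it concerns a secondary endpoint. The primary OS analysis and the 109-death design are untouched. The 6.2.1 wording is a minor inconsistency with a clear resolution.

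**What to change.** - In SAP 7.4.2, state that censoring at day 1 applies only to subjects with neither an evaluable post-baseline scan nor an on-study death, and that this holds for all randomized subjects, dosed or not.
- In the early-death sentence of SAP 10.1.2, replace enzalutamide by study drug, or extend the sentence to all randomized subjects so that those never dosed are covered.
- In SAP 6.2.1, replace enzalutamide by study drug in the treatment-emergent window, to match SAP 7.5 and the protocol.

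The cost is three wording edits, with no new data and no change to sample size or power. SAP 1 allows revisions only before hard lock, and protocol Appendix 12.9 reports that the primary analysis has been done. If lock has passed, the sponsor should confirm which early-death rule was programmed, report the number of such deaths by arm, and record any departure from the SAP in the clinical study report.

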6.2.2 Laboratory Assessments

Routine laboratory samples for hematology, biochemistry, coagulation, viral load (if applicable), pregnancy and urinalysis will be collected and analyzed at the Institution’s local laboratory. The local laboratory must be accredited to perform the protocol required tests and a certificate of accreditation and laboratory normal ranges must be provided to the Sponsor.

6.2.3 Vital Signs

Vital signs will include systolic and diastolic blood pressure (mmHg), radial pulse (beats/min) and temperature.

Change from baseline, defined as the post-baseline value minus the baseline value will be calculated for each assessment.

6.2.4 Electrocardiogram (ECG)

A 12-lead ECG will be performed and parameters that include heart rate, PR interval, RR interval, QRS interval, QT interval will be collected.

Abnormalities and clinical significance as judged by the Investigator will be reported as well.

6.2.5 Other Safety-Related Observations

6.2.5.1 ECOG

ECOG performance status data are collected according to Schedule of Assessment.

6.3 Pharmacokinetic Variables

Pharmacokinetic variables include pre-dose plasma concentrations of enzalutamide, its active metabolite N-desmethyl enzalutamide, and sum of enzalutamide plus N-desmethyl enzalutamide.

6.4

[REDACTED]

[REDACTED]

[REDACTED]

[REDACTED]

6.5 Other Variables

6.5.1 Previous and Concomitant Treatment

Previous medication is defined as a medication with at least one dose taken before the date of first dose of study drug. Concomitant medication is defined as a medication with at least one dose taken after the date of first dose (inclusive). According to the protocol, concomitant medications were to be recorded up to the 30-Day Follow-up visit.

6.5.2

[REDACTED]

7 STATISTICAL METHODOLOGY

7.1 General Considerations

In general, all data will be summarized with descriptive statistics (number of subjects, mean, median, standard deviation (SD), minimum, and maximum) for continuous endpoints, and frequency and percentage for categorical endpoints.

For continuous variables, descriptive statistics will include the number of subjects (n), mean, standard deviation, median, minimum and maximum. When needed, the use of other percentiles (e.g. 10%, 25%, 75% and 90%) will be mentioned in the relevant section.

Frequencies and percentages will be displayed for categorical data. Percentages by categories will be based on the number of subjects with no missing data, i.e. will add up to 100%.

For time to events variables (OS, PFS and [REDACTED]), descriptive statistics will include the number of subjects (n), the number of events, the number of censored subjects, median time and 95% CI. Kaplan-Meier plots will also be generated.

Summaries based on FAS (e.g. baseline and efficacy data) will be presented, unless specifically stated otherwise. Safety analysis and other summaries based on SAF will be presented.

All data processing, summarization, and analyses will be performed using SAS® Version 9.3 or higher on Unix. Specifications for table, figures, and data listing formats can be found in the TLF specifications for this study.

7.2 Study Population

7.2.1 Disposition of Subjects

Number and percentage of subjects with informed consent, enrolled, discontinued before enrollment will be presented for all subjects.

The following subject data will be presented for the All Randomized Subjects:

- Number and percentage of subjects in each analysis set;
- Number and percentage of subjects discontinued treatment, by primary reason for treatment discontinuation;
- Number and percentage of subjects discontinued study, by primary reason for study discontinuation;
- Number and percentage of subjects completed the study.

7.2.2 Protocol Deviations

Protocol deviations as defined in the study protocol (Section 7.8 Protocol Deviations and Other Analyses) will be assessed for the FAS. The number and percentage of subjects meeting any criteria will be summarized for each criterion and overall as well as by study site. Subjects deviating from a criterion more than once will be counted once for the corresponding criterion. Any subjects who have more than one protocol deviation will be counted once in the overall summary. A data listing will be provided by site and subject.

The protocol deviation (PD) criteria will be uniquely identified in the summary table and listing. The unique identifiers will be as follows:

PD1 - Entered into the study even though they did not satisfy entry criteria,

PD2 - Developed withdrawal criteria during the study and was not withdrawn,

PD3 - Received wrong treatment or incorrect dose,

PD4 - Received excluded concomitant treatment.

7.2.3 Demographic and Other Baseline Characteristics

Number and percentage of subjects enrolled in each country and site will be presented for the FAS.

For demographics table, descriptive statistics for age, sex, race, ethnicity, weight, body mass index (BMI), height, and history of smoking and alcohol use at study entry will be presented by treatment group. Frequency tabulations for ethnicity, age group and race will be presented by treatment group. This will be done for the SAF and FAS populations. Descriptive statistics will include number of subjects, mean, standard deviation, minimum, median and maximum for continuous endpoints, and frequency and percentage for categorical endpoints.

For disease history table, descriptive statistics for time from initial diagnostic will be presented by treatment group. Frequency tabulations for histopathology at diagnosis, histologic grade, anatomic staging/prognostic category at initial diagnosis, primary tumor stage, regional lymph node stage, distant metastasis, Barcelona Clinic Liver Cancer (BCLC) stage at screening will be presented by treatment group. Disease history will be summarized by descriptive statistics for the FAS.

HCC etiology factors, presence/absence of cirrhosis, prior systemic treatment for HCC with sorafenib or other anti-VEGF therapy, confirmed disease progression or discontinuation of sorafenib due to intolerance, child-pugh scoring, and HBV/HCV status will be summarized by treatment group for the FAS.

Medical history is coded in MedDRA, and will be summarized by System Organ Class (SOC) and Preferred Term (PT) as well as by PT alone, for the SAF.

7.2.4 Previous and Concomitant Medications

Previous medications are coded with WHO-DD, and will be summarized by therapeutic subgroup (ATC 2nd level) and chemical subgroup (ATC 4th level) and preferred WHO name for the SAF. Prior HCC treatment will also be summarized for the FAS.

As with previous medication, concomitant medication are coded with WHO-DD, and will be summarized by therapeutic subgroup (ATC 2nd level) and chemical subgroup (ATC 4th level) and preferred WHO name for the SAF. Subjects taking the same medication multiple times will be counted once per medication and investigational period. A medication which can be classified into several chemical and/or therapeutic subgroups is presented in all chemical and therapeutic subgroups.

7.3 Study Drugs

7.3.1 Exposure

The following information on drug exposure will be presented for the SAF:

- Descriptive statistics for cumulative amount of the drug a subject was exposed to and average daily dose; and
- Number and percent of subjects with dose increase, decreases or interruptions.

Duration of exposure (defined in days as the date of last dosing - the date of first dosing + 1) will be summarized in two ways.

- Descriptive statistics will be presented.
- Exposure time will be categorized according to the following categories by study drug:
 - less than 3 months
 - at least 3 months and less than 6 months
 - at least 6 months

Counts and percentages of subjects in each of these categories will be summarized for the SAF.

7.3.2 Treatment Compliance

Overall compliance with the dosing schedule will be examined for subjects in the SAF whose total study drug count and first and last days of treatment are known.

Percent overall compliance (defined as the percentage of the total study drug taken over total planned study drug doses) for Enzalutamide and placebo will be summarized in two ways for the SAF:

- Descriptive statistics will be presented by study drug.
- Percent compliance will be categorized according to the following categories by study drug:
 - less than 80%
 - at least 80%, less or equal to 90%
 - at least 90%, less or equal to 100%
 - greater than 100%

7.4 Analysis of Efficacy

All efficacy analysis will be performed using the FAS unless otherwise stated.

7.4.1 Analysis of Primary Endpoint(s)

The primary endpoint, OS will be defined as the time from the date of randomization until the documented date of death from any cause. Subjects who are still alive at the time of the data cutoff date will be censored on the last date known to be alive or at the data cutoff date, whichever occurs first.

The null hypothesis is that OS distributions of the 2 arms are equivalent. The alternative hypothesis is that OS is prolonged in enzalutamide arm.

The null hypothesis will be tested using a stratified one-sided log-rank test at the 0.10 level (stratified by geographic region and ECOG performance status). The hazard ratio of the treatment effect along with two-sided 95% CI will also be calculated using a Cox proportional hazard model, stratified by geographic region and ECOG performance status. In addition, an 80% two-sided confidence interval will also be provided to correspond to the 0.1 one-sided alpha level for the primary analysis. Unstratified analysis will be performed too as sensitivity analysis.

A sensitivity analysis same as primary analysis but for subjects randomized and treated will be performed if needed, depending on number of patients randomized and not treated, this analysis will be decided at the Final Data Review meeting if needed.

